### 13.2. Sampling and non-response bias and missing data

We will perform an intention-to-treat analysis. The analysis will include all patients in the groups and time period which they were randomly assigned to begin receiving treatment, regardless of their adherence with the treatment and/or subsequent participation. An adjusted odds ratio will be estimated to compare control and intervention group odds of 180-day readmission or death, and adjustment mean differences will be estimated to compare control and intervention group means for CCQ Total Score and VR-12 PCS. In the event of missing outcome data, the primary analysis of the respective outcome will be based on outcome data imputed under a multiple imputation using chained equations procedure, with inference from 70 models of imputed data combined using Rubin's Rules. Sensitivity complete-case analyses will be performed for outcomes with missing values to assess whether direction of association or statistical significance is impacted by a change in missing data approach.

### 13.3. Sample size and study power

For the sample size calculation, let the design have  $I$  clusters,  $T$  time points, and  $N$  individuals sampled per cluster per time interval. Assume the model,  $Y_{ij} = \mu + \alpha_i + \beta_j + X_{ij}\theta + e_{ij}$ , where  $\alpha_i$  is a random effect for cluster  $i$  such that  $\alpha_i \sim N(0, \tau^2)$ ,  $\beta_j$  is a fixed effect corresponding to time interval  $j$ ,  $X_{ij}$  is an indicator of the treatment mode in cluster  $i$  at time  $j$  (1=intervention; 0=control),  $\theta$  is treatment effect and  $e_{ij} = \sum_k e_{ij}/N$  are independent and identically distributed  $N(0, \sigma^2)$  and  $\sigma^2_e/N$ . Let  $Y_{ij}$  be the mean for cluster  $i$  at time  $j$ .

Assume testing the hypothesis  $H_0: \theta = 0$  versus  $H_A: \theta = \theta_A$ , where  $\theta_A$  is the treatment effect size. The

approximate power for conducting a two-tailed test of size alpha is  $power = \Phi\left(\left(\theta_A/\sqrt{Var(\hat{\theta})}\right) - Z_{1-\alpha/2}\right)$

where  $\Phi$  is the cumulative standard normal distribution function,  $Z_{1-\alpha/2}$  is the  $(1 - \alpha/2)$ th quantile of the standard normal distribution function and  $\hat{\theta}$  is the estimated treatment effect size. Let  $X_{ij} = 0$  if cluster  $i$  receives the control at time  $j$  and let  $X_{ij} = 1$  if cluster  $i$  receives the intervention at time  $j$ . Thus with this matrix  $\mathbf{X}$  and assuming equal  $N$  per cluster per time interval, then assume  $Var(\hat{\theta}) = [I\sigma^2(\sigma^2 + T\tau^2)]/[(IU - W)\sigma^2 + (U^2 + ITU - TW - IV)\tau^2]$  where  $U = \sum_{ij} X_{ij}$ ,  $W = \sum_j (\sum_i X_{ij})^2$  and  $V = \sum_i (\sum_j X_{ij})^2$ . This variance equation is used in the power calculation. We have approached the power estimates conservatively allowing for a lower proportion of subjects who may experience hospital readmissions, allowing for regression to the mean.

We assume 30 unidirectional movements from control to intervention among 30 clusters (clinics) and 15 individuals sampled per cluster per time interval. We assume a significance level of alpha = 0.05. We assume baseline hospital readmission of 0.40 with a 10% relative reduction to 0.36, baseline CCQ of 0.40 with a 10% relative reduction to 0.36, and baseline SF-12 of 0.35 with an 11% relative increase to 0.39. We assume each outcome to have a coefficient of variation equal to 0.1. Under these assumptions, our power is estimated for hospital readmission, CCQ, and SF-12 analyses to be 0.874, 0.874, and 0.889, respectively.

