## 12.1. Primary outcome measures

**Hospital readmission and mortality:** assess 180 days after the index discharge with a composite measure of any hospital readmission or death.

**COPD specific health status:** measured with the *Clinical COPD Questionnaire (CCQ)*, which consists of 10 items that encompass three domains (symptoms, functional state, mental state). Scores range from 0-to-6 with higher scores indicating better health. The minimally important difference (MID) is 0.39 with a standard error of 0.21.

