## 13. Analytic Approach

---

Our modified stepped wedge design, through its randomized intervention allocation, offers several advantages to interval validity compared to observational approaches. However, our clustered design also requires additional analytic evaluation compared to a simple two-arm randomized trial. The primary outcome measure is COPD hospital readmission/mortality within 180 days as assessed through the CDW. Time zero for intervention patients is the start of the period when the provider cluster is randomized to receive the intervention. Time zero for control patients is the start of each 30-day period (wedge) while the provider cluster remained unexposed to the intervention. Provider clusters randomized to receive the intervention at later time periods will accrue fewer patients than clusters randomized to earlier periods. We will present the analysis for hospital readmission as the example for the analytic approach that would also apply for our secondary outcome measures.

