### **15. Summary of Changes from original protocol**

---

- 2/12/2014: VA CDW:
  - Used instead of Veterans Integrates Service Network (VISN) 20 data warehouse because of changes in VA policy.
- 2/12/2014: Remuneration
  - Patient participants were remunerated \$20 instead of \$25 based on budget and IRB application.

- 3/5/2015: Provider enrollment
  - Modified to passively consent providers who had not responded to invitation after one week.
- 4/2/2014: Outcomes
  - Used VR-12 instead of the SF-12 because VR-12 is the SF-12 modified for a Veteran population.
- 2/12/2014: Wedge interval length/outcomes period:
  - Wedges consisted of 30-day wedge intervals instead of 1 month to maintain standard interval length.
  - 30-day intervals resulted in 180-day outcomes period instead of six months.
- 5/6/2014: Number of wedges
  - Used 30 wedges over 30 months instead of 36 wedges over 36 months;
  - Recalculated power estimates based on actual numbers of consented providers and COPD exacerbation discharge data. To maintain 0.90 power assuming an alpha of 0.95 and coefficient of variation of 0.1, we would require 30 clusters in lieu of 36.
- 5/21/2015: Smoking status self-report
  - Added short smoking status questionnaire with patient outcomes, as smoking status around the time of discharge is an indicator of quality of COPD care.
- 8/4/2016: COPD Training for inpatient discharge and primary care teams
  - After several attempts to coordinate in-services to inpatient and primary care teams, we were unable to develop a practical and mutually agreeable schedule because of logistical and scheduling constraints.
- 7/23/2015: Mailed patient outcomes
  - Added option for patient participant to complete surveys via mail instead of telephone.
- 3/22/2016: E-cigarettes and vaping
  - Included a question about e-cigarette and vaping use, as these devices' popularity increased and many Veterans had adopted these practices over cigarette smoking.
- 7/27/2017: Qualitative interviews
  - Initially targeted providers after three intervention discharge; because of low response rate we reduced to one in attempt to include more providers.
- 1/12/18: Correlation of measures within patient/used participants first DC only

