  - We did not correlate measures within patient, because we used only the first index discharge per patient. Given the small number of patients with > 1 index discharge, the additional complexity of modeling within-patient correlation would not be cost-effective with respect to degrees of freedom.
- 7/27/18: VR-12 PCS
  - demoted from primary to secondary because COPD intervention studies have not shown effects on QoL so no good rationale that there will be any significant effect- we will not adjust for it.
- 12/28/18: Analyses
  - Modeling time: we originally wanted to model  $(k - 1)$  fixed effects for the  $k$  wedges in the stepped-wedge design. However, each wedge only had ~10 discharges, on average, and it would be expensive (and likely not very informative) to model all of the wedges individually. Therefore, we modeled time using a 3-knot restricted (or natural) cubic spline for flexibility and lower degrees of freedom cost.
  - Medicare data: not used because of insufficient time/resources to pull and merge with current data.

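### Section 13.3 states power of 0.874 on 15 discharges per cluster per interval; the plan later reports about 10 per wedge, which most likely means power near 0.08, and never reconciles the two

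*Combined protocol and SAP*

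**What the plan says.** Section 13.3 states: "We assume 30 unidirectional movements from control to intervention among 30 clusters (clinics) and 15 individuals sampled per cluster per time interval". It takes readmission of 0.40 falling to 0.36, a coefficient of variation of 0.1 and a two-tailed test at alpha 0.05, and concludes that "our power is estimated for hospital readmission, CCQ, and SF-12 analyses to be 0.874, 0.874, and 0.889, respectively". The section describes its approach to power as conservative.

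The 12/28/18 entry in Section 15 explains why the fixed effects for individual wedges were dropped in favour of a restricted cubic spline: "each wedge only had ~10 discharges, on average", so that "it would be expensive (and likely not very informative) to model all of the wedges individually". The spline is the model now in Section 13.1.

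Section 13 uses the word wedge for the 30-day period. The 2/12/2014 entry in Section 15 does the same: "Wedges consisted of 30-day wedge intervals instead of 1 month". Section 12.1 defines the first primary outcome as follows: "assess 180 days after the index discharge with a composite measure of any hospital readmission or death".

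**The concern.** The two counts sit in the same document and differ by up to a factor of 45 (450 against about 10 per 30-day period). The model section was changed in response to the low count, but the power section was not. Section 13.3 is the plan's only current account of what the trial can detect. A reader who takes 87% power at face value would treat a non-significant result as good evidence against a 4-point reduction in readmission. At the reported count such a result could not exclude that reduction, or one several times larger.

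In addition, the power is for readmission alone, and the documents give no expected rate for readmission or death.

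**Working it through.** **Inputs from the plan.** I = 30 clusters, one crossing per step (Sections 7 and 13.3). T = 31 time points, inferred from Section 7: period 0 plus 30 steps. p0 = 0.40, p1 = 0.36, CV = 0.1, two-sided alpha 0.05 (Section 13.3). From these, τ = 0.1 × 0.40 = 0.04 and τ² = 0.0016. The within-cell variance is σ² = p̄(1 − p̄)/N with p̄ = 0.38, that is 0.2356/N.

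**Formula (Section 13.3).** Var(θ̂) = Iσ²(σ² + Tτ²) / [(IU − W)σ² + (U² + ITU − TW − IV)τ²], and power = Φ(θ/SE − 1.96).

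With one cluster crossing per step, U = 465 and W = V = 9,455. Hence IU − W = 13,950 − 9,455 = 4,495, and U² + ITU − TW − IV = 216,225 + 432,450 − 293,105 − 283,650 = 71,920.

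**Reproducing the printed figure, N = 15.** σ² = 0.015707. Var = 30 × 0.015707 × (0.015707 + 0.0496) / (4,495 × 0.015707 + 71,920 × 0.0016) = 0.03077/185.67 = 0.0001657. SE = 0.01287, and power = Φ(3.107 − 1.96) = 0.874. The same steps for SF-12 (0.35 to 0.39) give SE 0.01257 and power 0.889. Both match, so N is the count in each of the 30 × 31 = 930 cluster-period cells: 15 × 30 = 450 per interval and 15 × 930 = 13,950 in total.

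**What about 10 per wedge means.** The entry does not say that the count is over all clusters. Four points favour that reading:
- Section 13 and the 2/12/2014 entry use wedge for the 30-day interval.
- The 12/28/18 entry counts k − 1 fixed effects for k wedges, so wedges are time periods and not cluster-period cells.
- The entry calls those effects costly in degrees of freedom. With 10 per cluster-interval there would be 9,300 discharges and about 30 time effects would cost little; with about 310 the remark makes sense.
- Section 10.1 has one team review every new intervention discharge each week. Once all clusters have crossed, 450 per 30 days is 450 × 7/30 = 105 patients a week and 300 is 70; 10 is 2 to 3.

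On this reading N = 10/30 = 1/3 per cell, and the total is 10 × 31 = 310.

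**Power at N = 1/3.** σ² = 0.7068. Var = 30 × 0.7068 × (0.7068 + 0.0496) / (4,495 × 0.7068 + 115.07) = 16.04/3,292.1 = 0.00487. SE = 0.0698, and power = Φ(0.573 − 1.96) = 0.083. The 95% half-width is 1.96 × 0.0698 = 0.137. Solving for 80% power with p̄ updated gives a detectable difference of 0.186 (0.40 to about 0.21).

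| Reading or variation | Readmission power |
|---|---|
| 15 per cell (13,950) | 0.874 |
| 10 per cluster per interval (9,300) | 0.744 |
| 10 per interval over all clusters (310) | 0.083 |
| 10 per cluster over the whole trial (300) | 0.081 |
| 5 to 20 per interval over all clusters | 0.060 to 0.123 |
| 310, between-cluster SD from 0.12 down to 0 | 0.076 to 0.084 |
| 310, individually randomised two-arm comparison | 0.11 |

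For 80% power at 4 points, N must be about 11.8 per cell: 353 per interval, about 10,950 in total.

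**Checks.** At a third of a discharge per cell the closed form is approximate. Placing 310 discharges at random in 930 cells leaves about 72% of them empty. Generalised least squares on such layouts (200 draws, cluster SD 0.04) gives power 0.079 with period effects and 0.082 with three spline terms. With equal cells, spline time in place of period effects leaves 0.083 unchanged.

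**Composite outcome.** No rate is given, so assume a baseline of 0.50 to 0.60 and a 10% relative reduction. Power is 0.10 to 0.13 at about 310 discharges, and 0.87 to 0.95 at 10 per cluster per interval.

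**The case against.** The 0.874 is correct on its own inputs, and Section 13.3 words it as conditional on them; a planning calculation does not become false because accrual fell short. The count of about 10 appears only in the summary of changes and the plan never says that it pools clusters. If it were per cluster per interval, power would be 0.74 for readmission, and the composite could be adequately powered. The figures here are risk differences from a model with 30 cluster effects, whereas Sections 13.1 and 13.2 plan an adjusted odds ratio with provider random effects and two covariates. The entry is dated after follow-up should have ended, so no design choice remains open. The 5/6/2014 entry also says that power was recalculated from actual discharge data.

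Parts of this stand. The pooled reading is an inference, the shortfall for the composite depends on it, and ±14 points is a guide to precision, not the interval that the trial will report. The rest does not remove the conflict. The count is an observed fact that supports the current model, not superseded text. The 5/6/2014 recalculation predates the first control period of May 12, 2015 and gives no count per cluster-interval. On every reading considered, readmission power is below the printed 0.874. A conditional statement still misleads when the same document shows that its key condition was not met and does not say so.

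**Conclusion.** The concern holds and must be fixed. The stated power for readmission requires 15 discharges per cluster per interval, and the plan's own later count contradicts that. On the best-supported reading the shortfall is about 45-fold, and power for 0.40 versus 0.36 is about 0.08, not 0.874. On the most favourable reading it is 0.74.

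The 0.08 assumes 31 periods, even accrual over clusters and periods, the plan's coefficient of variation of 0.1, about 10 taken at face value as a count over all clusters, and no gain from covariate adjustment. It barely changes with the between-cluster variance or the form of the time effect. That the two counts are unreconciled is certain; the exact power awaits the sponsor's confirmation of what the count covers.

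**What to change.** Amend Section 13.3 as follows.

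- Keep the 15-per-cluster figure and its powers, labelled as the original planning assumption, which was not met.
- Add the realised count per 30-day interval, state whether it is over all clusters, and give the total.
- If the total is about 310, state that power for 0.40 versus 0.36 is about 0.08, that the difference detectable with 80% power is about 19 points (0.40 to about 0.21), and that the expected 95% confidence interval half-width is about 14 points. If the total differs, recompute these with the same formula.
- State that the calculation covers readmission only, and give the baseline rate assumed for readmission or death.
- Say that the trial should not be described as having 87% power, and that the primary result, including a null one, will be interpreted from its confidence interval.

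The cost is SAP wording and a less favourable stated figure. No extra patients, no change to data collection and no change to the analysis model are needed.

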### 13.1. Models

We will use mixed-effects linear regression or logistic regression as appropriate for the outcome of interest (180-day readmission or death, CCQ Total Score, VR-12 PCS) with clustering by provider:  $g(E(y_i|\mathbf{X}_i, \alpha_{j[i]}) = \mathbf{X}_i\beta + \alpha_{j[i]}$ , where  $y_i$  is the outcome for patient  $i$  and  $\alpha_{j[i]}$  is a random effect for provider  $j$  seen by patient  $i$  such that, across providers, the  $\alpha_{j[i]}$ 's are assumed independently and identically distributed (i.i.d.)  $Normal(0, \sigma_\alpha^2)$ .  $\beta$  is a  $7 \times 1$  vector of fixed effects regression coefficients, and  $\mathbf{X}_i$  is a  $1 \times 7$  vector containing the following fixed effects terms for patient  $i$ : a constant term (identical across patients), an indicator for patient  $i$ 's receipt of the intervention ( $X_i^{Intervention} = 1$  if patient  $i$  received the intervention,  $X_i^{Intervention} = 0$  otherwise), three time-based restricted cubic spline terms for patient  $i$ , the number of days in the past year that patient  $i$  was exposed to systemic corticosteroids, and the number of COPD exacerbations not requiring admission experienced by patient  $i$  in the past year. The logistic link function was used for the 180-day readmission or death GLMM such that  $E(y_i|\mathbf{X}_i, \alpha_{j[i]}) = \pi_i = (e^{\mathbf{X}_i\beta + \alpha_{j[i]}})/(1 + e^{\mathbf{X}_i\beta + \alpha_{j[i]}})$ . The identity link function was used for the CCQ Total Score and VR-12 PCS GLMMs such that  $E(y_i|\mathbf{X}_i, \alpha_{j[i]}) = \mu_i = \mathbf{X}_i\beta + \alpha_{j[i]}$ .

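### The CCQ and SF-12 power figures in section 13.3 come from inputs that behave as proportions, but both outcomes are scores to be compared as means

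*Combined protocol and SAP*

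**What the plan says.** Section 13.3 gives a stepped-wedge variance formula and applies it to three outcomes. Readmission is assumed to fall from 0.40 to 0.36. For the other two the inputs are "baseline CCQ of 0.40 with a 10% relative reduction to 0.36, and baseline SF-12 of 0.35 with an 11% relative increase to 0.39". One variability assumption covers all three: "We assume each outcome to have a coefficient of variation equal to 0.1". The result is that "our power is estimated for hospital readmission, CCQ, and SF-12 analyses to be 0.874, 0.874, and 0.889, respectively".

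The outcomes and their analysis are defined elsewhere:

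- Section 12.1, on CCQ: "Scores range from 0-to-6 with higher scores indicating better health". The same paragraph adds: "The minimally important difference (MID) is 0.39".
- Section 12.2 makes the VR-12 PCS a 0-to-100 score and cites a national mean of 27.0 and SD of 8.4 for Veterans admitted for COPD.
- Section 13.1: "The identity link function was used for the CCQ Total Score and VR-12 PCS GLMMs".
- Section 13.2: "adjustment mean differences will be estimated to compare control and intervention group means for CCQ Total Score and VR-12 PCS".

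**The concern.** A CCQ baseline of 0.40 that moves by 0.04 is a natural input for a proportion. It is an odd one for a 0-to-6 score whose minimally important difference is 0.39, since 0.04 is about a tenth of that. A baseline of 0.35 for a score with mean 27.0 is odder still. The CCQ inputs and result are the same as those for readmission, which is binary. The only outcome that section 13.3 describes as a proportion is readmission, where it speaks of "allowing for a lower proportion of subjects who may experience hospital readmissions".

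CCQ is listed as a primary outcome in section 12.1, and improving it is half of the goal in section 5. If its power figure belongs to a different kind of outcome, a reader cannot tell what CCQ difference the trial was planned to detect, or what a null CCQ result would rule out.

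**Working it through.** **Inputs from section 13.3.** I = 30 clusters, 30 one-way crossings, N = 15 per cluster-period, two-sided alpha 0.05. With the all-control period 0 in section 7, T = 31.

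**Design constants.** With one cluster crossing per period, U = 465 and W = V = 9,455. So IU − W = 13,950 − 9,455 = 4,495, and U² + ITU − TW − IV = 71,920.

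**Formula.** Var(θ̂) = Iσ²(σ² + Tτ²) / [4,495σ² + 71,920τ²], where σ² is the patient variance divided by N. Power = Φ(θ/SE − 1.96).

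**Step 1: reproduce the stated figures as proportions.** Take the patient variance as p(1 − p) at the average of the two values, and τ as 0.1 × baseline.

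- *CCQ, and identically readmission:* σ² = 0.38 × 0.62/15 = 0.015707; τ = 0.04. Var = 30 × 0.015707 × (0.015707 + 0.0496) / (70.60 + 115.07) = 0.0001657. SE = 0.01287; 0.04/SE = 3.107; power = 0.8743 (stated 0.874).
- *SF-12:* σ² = 0.37 × 0.63/15 = 0.01554; τ = 0.035. Var = 30 × 0.01554 × (0.01554 + 0.037975) / (69.85 + 88.10) = 0.0001580. SE = 0.01257; 0.04/SE = 3.183; power = 0.8893 (stated 0.889).

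Other choices (T = 30, variance at either value, τ from either value) give 0.864 to 0.890 for CCQ and 0.869 to 0.895 for SF-12.

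**Step 2: what patient SD do the stated figures imply?** Solving the formula for the SD that yields power rounding to the stated value:

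| Row | Implied SD | Binomial SD | Implied SD if the score was rescaled to 0–1 |
|---|---|---|---|
| CCQ | 0.4852–0.4861 | 0.4854 | × 6 = 2.91–2.92 CCQ points |
| SF-12 | 0.4826–0.4836 | 0.4828 | × 100 = 48.3–48.4 PCS points, against 8.4 in section 12.2 |

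**Step 3: other readings.**

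- Coefficient of variation of 0.1 as the patient-level spread of a rescaled CCQ (SD = 0.1 × 0.40 = 0.04): power about 1.00, not 0.874.
- PCS rescaled to 0–1 with the documented SD (0.084) and τ = 0.035: power about 1.00, not 0.889.
- A literal 0.04-point change: CCQ power 0.15 to 0.41 (assumed SD 0.8 to 1.5), PCS power 0.036 (SD 8.4, τ 2.7).

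None of these gives the stated figures.

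**Step 4: the same formula on the score scales.** The documents give no CCQ SD or mean. I assume a patient SD of 0.8 to 1.5 and τ of 0.2 to 0.4 (0.1 × an assumed mean of 2 to 4). For PCS, the SD of 8.4 is documented, τ = 0.1 × 27.0 = 2.7, and the target is 0.11 × 27.0 = 2.97 points. The difference detectable with 80% power is 2.80 × SE.

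| Outcome, target | N | SE | Power | Detectable at 80% power |
|---|---|---|---|---|
| CCQ, 0.39 | 15 | 0.0231–0.0434 | about 1.00 | 0.065–0.122 |
| PCS, 2.97 | 15 | 0.2443 | about 1.00 | 0.68 |
| CCQ, 0.39 | 7.5 | up to 0.0607 | about 1.00 | 0.09–0.17 |
| PCS, 2.97 | 7.5 | 0.3424 | about 1.00 | 0.96 |

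Two worked cases at N = 15:

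- *CCQ, SD 1.5, τ 0.4:* σ² = 2.25/15 = 0.15. Var = 30 × 0.15 × (0.15 + 4.96) / (674.25 + 11,507.2) = 0.001888, so SE = 0.0434.
- *PCS:* σ² = 70.56/15 = 4.704. Var = 30 × 4.704 × (4.704 + 225.99) / (21,144 + 524,297) = 0.05969, so SE = 0.2443.

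The N = 7.5 rows assume that half of those sampled return the survey; the documents give no response rate.

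**The case against.** The best defence is that 0.40 and 0.35 are mean scores rescaled to 0–1. For a variable bounded by 0 and 1, p(1 − p) is the largest variance possible at a given mean. On that reading 0.874 would be roughly a worst-case power for a shift of 0.04 × 6 = 0.24 CCQ points. This is coherent, but the plan states no such rescaling, and its remark about being conservative names only readmission. For PCS the reading also needs an SD of about 48 points where the plan itself cites 8.4.

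Second, the values near 1.00 rest on an assumed CCQ SD and mean, and on a different target from the plan's 10% relative change. Both points are fair. With a 10% change in the assumed CCQ mean instead, power is still 0.997 or higher.

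Third, they also depend on N = 15. Section 15 reports only about 10 discharges per wedge, roughly one third of a patient per cluster-period if spread over 30 clusters. The formula then gives 0.37 to 0.87 for CCQ at 0.39 and 0.58 for PCS at 2.97. This stands as a caution against quoting 1.00 as achieved power. Low accrual affects readmission too, and is a separate matter.

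Fourth, the practical consequence is small. The readmission row has suitable inputs and reproduces, section 15 records the replacement of SF-12 by VR-12, and PCS is now secondary. That limits the weight of the point without making the CCQ figure right.

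**Conclusion.** The concern holds. The arithmetic in section 13.3 is sound for proportions, but 0.874 and 0.889 do not describe the planned CCQ and PCS analyses. They were almost certainly computed as proportions, and the CCQ figure is the readmission calculation repeated.

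This is a documentation error that should be fixed, chiefly because CCQ is a primary outcome. It does not show that the trial was planned with too little power: on the assumptions in the working, and at the planned N, score-scale power for the targets considered is above the stated figures. No single corrected CCQ value can be given, because the plan supplies neither an SD nor a target mean difference. No estimate, imputation or test is affected.

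**What to change.** In section 13.3, withdraw 0.874 for CCQ and 0.889 for SF-12, and keep the readmission row. Restate the two score outcomes with the formula already there, giving for each:

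- the patient SD and its source (for PCS, mean 27.0 and SD 8.4 from section 12.2);
- the between-cluster SD in score points;
- the target mean difference (for CCQ, for example, the 0.39 in section 12.1);
- the expected number of survey responders per cluster-period.

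Rename the SF-12 row VR-12 PCS. Reconcile the sign of the CCQ target with section 12.1: section 13.3 plans a reduction, while section 12.1 says that higher scores are better. If responder proportions were intended, define them and align sections 13.1 and 13.2 with them.

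For the score-scale restatement, the cost is a recalculation and a few sentences in section 13.3. The restated power may differ from the present figures; data collection, models and estimates do not change.
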